Cardiogoniometry for Detecting Coronary Artery Disease by CT Angiography

NCT02725671

April 3, 2015

JHM IRB - eForm A – Protocol

1. Abstract

Cardiogniometry is a technique to process and evaluate vectorcardiography from regular ECG acquisitions. Vectorcardiography has a long tradition in cardiology for providing comprehensive information on myocardial function and integrity. Compared to standard electrocardiography, vectorcardiography has shown to be more sensitive to detect structural and ischemic heart disease. Unfortunately, the interpretation of vectorcardiography is complex which has hindered its widespread application. In recent years, computer assisted analysis has allowed automated interpretation of vectorcardiography with promising results in comparison to standard ECG for identifying patients with ischemic heart disease. However, the underlying mechanisms and threshold of altered cardiac vectors in the presence of coronary artery disease are not well understood. This research aims at exploring the relationship of computer assisted analysis of vectorcardiography with the presence, extent, severity, and location of coronary artery disease in comparison to standard ECG evaluation. Furthermore, we intent to follow up enrolled patients for the occurrence of adverse cardiovascular events for correlation with test findings. These data will provide comprehensive information on the diagnostic performance of noninvasive, inexpensive evaluation of cardiac vector loops for identifying patients at risk from coronary artery disease.

2. Objectives

- 1) Compare the diagnostic accuracy of cardiogniometry with standard ECG for detecting coronary artery disease as assessed by CT angiography
- 2) Investigate the relationship between abnormal cardiogniometry findings and the extent/severity/location of coronary artery disease by CT angiography
- 3) Compare the intermediate term prognosis of patients according to cardiogniometry, standard ECG, and CT findings

3. Background

Vectorcardiography has a long tradition in cardiology for the analysis of cardiac function and pathology.^{1,2} Numerous reports documented the utility of vectorcardiography for assessing myocardial ischemia, infarction, reperfusion, ventricular hypertrophy, and conduction abnormalities. In many instances, the diagnostic accuracy of vectorcardiography surpasses that of standard 12-lead surface electrocardiogram (ECG). However, traditional vectorcardiography is demanding in terms of both acquisition and interpretation skills and despite its good performance in experienced hands was never accepted by main stream cardiology practice. Cardiogniometry is a concept that utilizes only 4 leads to create a coordinate system allowing the analysis of cardiac vector loops including detailed description of its associated angles (“cardiogniometry”).^{3,4} Clinical studies have demonstrated remarkable consistency of these loop angles within healthy individuals over time.⁴ Deviations from established normal ranges indicate cardiac pathology. Several studies demonstrated good accuracy of cardiogniometry to identify patients with chronic ischemic heart disease and acute coronary syndromes.⁵⁻⁹ Test results in patients with ischemic heart disease do not seem to alter after revascularization procedures which may indicate that cardiogniometry detects permanent structural changes in the myocardium rather than acute ischemia.¹⁰ No adverse effects have been reported on the use of cardiogniometry and such effects are not expected given its nature as a

variant application of electrocardiography. The purpose of this investigation is to gather information on the relationship of cardiogoniometry findings and presence and extent of coronary atherosclerotic disease as well as its prognosis in comparison to standard 12-lead ECG acquisition. Specifically, we are interested in identifying a 'threshold' of atherosclerotic disease which may be associated with alteration of vector loop angles. Previous studies only used obstructive coronary artery disease by cardiac catheterization as end point but it is conceivable that cardiogoniometry vector loops are altered earlier in the process of ischemic heart disease. This would represent an advantage in early detecting patients at risk of adverse events using noninvasive testing without X-ray radiation or contrast exposure. Furthermore, we are interested in investigating the rate of adverse cardiovascular events in patients associated with abnormal cardiogoniometry results. We believe cardiogoniometry has the potential to be an inexpensive alternative or addition to current noninvasive tools for identifying patients at risk from coronary heart disease.

4. Study Procedures

- a. The sole study procedure is an ECG acquisition prior to a **clinical** cardiac CT acquisition. An ECG is not routinely acquired before cardiac CT and thus it will be done for investigational purposes. The ECG will be acquired using an investigational cardiogoniometry device. In addition to standard lead placement for 12-lead ECG, 4 leads will be placed on the chest and back specifically to acquire vector loops. In deviation of routine ECG recording, the patient will be asked to hold his breath for the duration of recording, i.e., approximately 20 seconds. The entire procedure is expected to be completed within 5 minutes. Baseline demographics, patient medical history, study results, and risk factors for coronary artery disease will be recorded.
- b. The study duration will be 5 years. No additional patient visits will be required. The only physical encounter with patients will be at the time of their cardiac CT acquisition which is performed for **clinical** reasons. The patients will be contacted by phone or email every 12 months to inquire about adverse cardiovascular events for the duration of the study.
- c. Interpretation of the ECG and cardiogoniometry findings will be performed without knowledge of any patient or imaging details. No other blinding will be performed.
- d. The regular clinical care will not be affected except for the addition of the ECG acquisition prior to the clinically performed cardiac CT.
- e. The study does not contain any treatment or patient management actions.

5. Inclusion/Exclusion Criteria

Patients age 18 or older who are referred for cardiac CT examination at the Johns Hopkins Hospital Division of Cardiology for evaluation of coronary artery disease will be asked to participate.

Patients may be referred for an outpatient CT scan, when hospitalized, or via the emergency room.

Exclusion criteria:

Patients with hemodynamic instability in whom CT scanning is performed emergently will be excluded from this study.

6. Devices

- a. An investigational cardiogoniometry device 'Cardiologic Explorer' manufactured by ENVERDIS will be used for this study. It is the only device of this kind available worldwide.
- b. The device is not FDA approved for clinical use in the US at this time.
- c. The device was inspected by the Clinical Engineering Services of the Johns Hopkins Hospital and no safety concerns to patients were found. The cardiogoniometry device is powered from a laptop computer via the USB port and during ECG recording the laptop will operate on battery

power only. Under these conditions, there is no electrical safety risk to the patient in case of device malfunction.

7. Study Statistics

- a. Primary outcome variable is the diagnostic accuracy of cardiogoniometry to identify patients with coronary artery disease as defined by CT coronary angiography in comparison to standard 12-lead ECG.
- b. Secondary outcome variables include the hazard of adverse cardiovascular events determined by cardiogoniometry in comparison to standard 12-lead ECG and CT coronary angiography, the diagnostic accuracy of cardiogoniometry to identify patients with high risk coronary anatomy or baseline myocardial perfusion abnormalities by CT angiography.
- c. Assuming an area under the curve value of 0.60 for standard ECG to identify patients with coronary artery disease and an anticipated value of 0.70 for cardiogoniometry, the required sample size will be 356 for a significance level of 0.05 and 80% power.
- d. No early stopping rules will be applied to assure maximum power for the proposed analyses.

8. Risks

- a. No major medical risks are known to be associated with the study procedure. Minor risks include a skin reaction to ECG lead adhesives.
- b. To minimize risk of skin reactions to ECG leads, patients will be asked regarding prior reactions and a skin wash using warm water will be offered if positive.
- c. No plans exist for deviations from the study plan.
- d. Legal risks include breach of confidentiality and unauthorized dissemination of patient data. To minimize such risk, all patient data will be stored on a designated laptop computer which will remain on hospital premises under personal supervision of the principal investigator. Data backup will occur on designated hard discs which will be securely stored in the PI's office.
- e. No known financial risks to the participants will arise from this study.

9. Benefits

- a. There will be no benefits to study participants as result of this study. Potential benefits to society will arise on the availability of a noninvasive, inexpensive tool for the assessment of coronary artery disease.

10. Payment and Remuneration

- a. There will be no compensation to patients for their participation in this study.

11. Costs

- a. The cardiogoniometry device to be used for this study was provided by the manufacturer. Costs for laptop computer and data storage will be carried by the principal investigator. ECG acquisition will be performed by the principal investigator or volunteer research staff. Costs for patient follow up will be carried by the principal investigator. When preliminary study results become available, an application for research funding will be submitted to funding agencies.

References

1. Hoffman I. Clinical vectorcardiography in adults. Part I. *Am Heart J.* 1980; 100: 239-254.
2. Hoffman I. Clinical vectorcardiography in adults. Part 2. *Am Heart J.* 1980; 100: 373-396.

3. Sanz E, et al. Cardiogoniometry. *Clin Cardiol.* 1983; 6: 199-206.
4. Saner H, et al. Cardiogoniometry: a new noninvasive method for detection of IHD. *Clin Cardiol.* 1983; 6: 207-210.
5. Huebner T, et al. Cardiogoniometric parameters for detection of CAD. *Med Biol Eng Comput.* 2010; 48: 435-446.
6. Tolg R, et al. Cardiogoniometry as a diagnostic tool in patients with ACS. *Clin Res Cardiol.* 2012; 101: 727-736.
7. Vontobel H, et al. Cardiogoniometry in CHD. A clinical study. *Schweiz Med Wochenschr.* 1988; 118: 1609-1611.
8. Meier A, et al. Comparative diagnostic value of a new computerized vectorcardiographic method (cardiogoniometry) and other noninvasive tests in medically treated patients with chest pain. *Clin Cardiol.* 1987; 10: 311-316.

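### The general exclusion of further blinding in section 4c covers the CT classification that defines disease, so nothing in the plan keeps study ECG and cardiogoniometry results from whoever makes it

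*Combined protocol and SAP*

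**What the plan says.** Section 4c contains the plan's only provision on blinding: "Interpretation of the ECG and cardiogoniometry findings will be performed without knowledge of any patient or imaging details. No other blinding will be performed". ECG and cardiogoniometry readers are therefore kept from patient and imaging information. The reverse direction, keeping the CT reader from the ECG and cardiogoniometry results, falls under the second sentence.

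Section 7a makes CT the reference: "Primary outcome variable is the diagnostic accuracy of cardiogoniometry to identify patients with coronary artery disease as defined by CT coronary angiography", compared with the standard ECG. CT findings are also the reference for the accuracy outcomes in 7b: "the diagnostic accuracy of cardiogoniometry to identify patients with high risk coronary anatomy or baseline myocardial perfusion abnormalities by CT angiography".

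Four other provisions bear on whether a CT reader could see a study result:

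- 4a and 4d place the recording before a clinically indicated CT. 4d adds: "The regular clinical care will not be affected except for the addition of the ECG acquisition prior to the clinically performed cardiac CT".
- 6b: "The device is not FDA approved for clinical use in the US at this time".
- 8d: "all patient data will be stored on a designated laptop computer which will remain on hospital premises under personal supervision of the principal investigator".
- 11a: "ECG acquisition will be performed by the principal investigator or volunteer research staff".

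No section says who reads the CT, who makes the classification used in the analysis, or whether a study result already exists at that moment.

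**The concern.** In an accuracy study the reference classification should be made independently of the tests being scored. If the person classifying the CT knows a test result and lets it settle a doubtful case, that test agrees with the reference for a reason unrelated to disease. Its accuracy is inflated, and the comparison with the other test shifts in its favour.

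The plan recognises this kind of leakage, because it masks the ECG and cardiogoniometry reads. It guards one direction only, and its general wording leaves the other direction unmasked. At stake are the primary comparison in 7a and the accuracy outcomes in 7b that also use CT findings as reference. Unmasked classification is hard to repair in the analysis afterwards, because no one will know which classifications were affected.

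**Working it through.** **Text.** I looked for any provision that limits the exclusion in 4c: an independent or central CT read, a rule withholding results, or a lock before linkage. There is none. 4d, 6b and 8d lower the chance of exposure: the CT belongs to usual care, the device is not approved for clinical use, and the data stay on a supervised laptop. None is a masking rule. 8d is written against breach of confidentiality and does not keep results from the person who supervises the laptop. 11a lets that same person acquire recordings, and nothing says that this person does or does not read CTs.

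**Illustration of size.** The plan gives no figure on this point, so there is none to reproduce. From 7c I take the accuracy of 0.60 assumed for the ECG (stated there as an area under the curve), the planned difference 0.70 − 0.60 = 0.10, and the sample size: "the required sample size will be 356 for a significance level of 0.05 and 80% power". The rest is assumed:

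- Both tests are read yes/no and each is truly correct with probability 0.60, so the true difference is zero.
- Correctness of the two tests has correlation r.
- A share b of all CT reads is set by the cardiogoniometry result; the remaining CT reads are correct.
- All 356 patients have both tests and a CT classification.
- The test is two-sided at 0.05, which is 2.5% in each direction.

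The tests disagree in a proportion D = 2 × 0.60 × 0.40 × (1 − r) = 0.48(1 − r) of patients, whatever the reader does. In the share b, every disagreement counts for cardiogoniometry; elsewhere disagreements split evenly. So:

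- spurious difference d = bD
- paired standard error SE = √(D/356)
- chance of a false significant result favouring cardiogoniometry = 1 − Φ(1.96 − d/SE)
- classifications changed = 0.40b

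For r = 0: D = 0.48 and SE = 0.0367. For r = 0.5: D = 0.24 and SE = 0.0260.

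| b | classifications changed (of 356) | d, r = 0.5 | d, r = 0 | false result, r = 0.5 | false result, r = 0 |
|---|---|---|---|---|---|
| 0 | 0 | 0 | 0 | 2.5% | 2.5% |
| 1% | 0.4% (about 1) | 0.0024 | 0.0048 | 3.1% | 3.4% |
| 2% | 0.8% (about 3) | 0.0048 | 0.0096 | 3.8% | 4.5% |
| 5% | 2% (about 7) | 0.012 | 0.024 | 6.7% | 9.6% |
| 10% | 4% (about 14) | 0.024 | 0.048 | 15.0% | 25.7% |

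Worked line for b = 10%, r = 0: d = 0.10 × 0.48 = 0.048; d/SE = 0.048/0.0367 = 1.31; 1 − Φ(1.96 − 1.31) = 0.257.

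Simulated McNemar tests (200,000 per setting, n = 356) at r = 0, 0.3 and 0.5 agree: 9.5%, 7.8% and 6.7% at b = 5%, and 25.8%, 19.2% and 15.2% at b = 10%.

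**Sensitivity.**

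- Higher correlation: at r = 0.8, D = 0.096 and SE = 0.0164. With b = 5%, d = 0.0048 and the chance is 4.8%.
- AUC scale, taken as (sensitivity + specificity)/2: at b = 10% the difference is unchanged at 50% prevalence and is 0.028–0.056 at 30% prevalence.
- Direction: if readers followed the ECG instead, the sign reverses (−0.024 to −0.048 at b = 10%). If influence were split evenly between the tests, the difference is zero.

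**The case against.** The strongest reply is that no route of exposure is shown. The CT is a clinical scan, the device is investigational, the data sit on one supervised laptop, and 4d says that only the acquisition is added to care. A clinical CT report shifted by a study result would sit badly with 4d. This stands as a reason to think exposure less likely. It does not close the gap: 4d would not cover a separate research classification, and none of these provisions withholds a result from the person who classifies the CT. They also do less for the 12-lead ECG, a familiar clinical test, than for the investigational output.

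A second reply is that 4c does not mention the CT read and may have been written with patients or treating staff in mind. That is fair. The accurate statement is that a general exclusion covers the CT read, not that the plan singled it out.

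A third is that the values of b are invented. They are. At 10% the model has an investigational surface recording settle one CT read in ten, always favouring one test. The lower rows of the table are as compatible with the documents as the upper ones. Both tests also come from one recording session, so a correlation above 0.5 is plausible and would shrink every figure.

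Two stronger readings are tempting and are not supported. A reader might infer that CT readers will see the cardiogoniometry output, or that the primary result will be biased towards cardiogoniometry; the documents establish neither. A reader might also infer that one and the same CT read serves 7a and 7b; the documents say only that CT findings are the reference in both.

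**Conclusion.** The point holds as a gap in a safeguard, not as a demonstration of bias. By its general wording, 4c leaves the reference classification for the primary outcome unmasked, and no other section limits that. Whether a study result reaches the person classifying the CT, which test would gain and by how much are all unknown.

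Under the stated assumptions the effect runs from none (results never seen) through slight (a false-positive chance of 3.1–4.5% if 1–2% of reads are set by cardiogoniometry) to serious (15.0–25.7% at 10%, with a spurious difference of up to about half the planned 0.10). It should be fixed because the remedy is small and the problem cannot reliably be undone once classifications have been made.

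**What to change.** Keep the first sentence of 4c and change the second to:

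> *The CT classification used for the study is made without access to the study cardiogoniometry and study-ECG results and is recorded and locked before it is linked to them. No other blinding will be performed.*

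This retains the plan's general statement on all other blinding. It governs only the classification used in the analysis and sets no rule on what clinical staff may see or do.

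The cost is coded file handling and delayed linkage, with no extra scans, visits or patients. If the person who acquires a recording also classifies that patient's CT, which the documents leave open, the output must stay hidden from that person until the classification is locked. If the roles are already separate in practice, the sentence simply records it.

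### Section 4c lets the 12-lead ECG be read with the cardiogoniometry output in view, so review bias in the primary paired comparison is not excluded

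*Combined protocol and SAP*

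**What the plan says.** Section 4c contains the whole blinding rule, in two sentences: "Interpretation of the ECG and cardiogoniometry findings will be performed without knowledge of any patient or imaging details. No other blinding will be performed". No other section adds separate readers for the two tests, a reading order, or the locking of one result before the other is opened.

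Section 4a describes one short procedure in one session: "The ECG will be acquired using an investigational cardiogoniometry device". Extra leads are placed for the vector loops. Section 6c has the device powered from a laptop, and Section 8d keeps all patient data on a designated laptop with backup.

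The primary outcome is in Section 7a: "Primary outcome variable is the diagnostic accuracy of cardiogoniometry to identify patients with coronary artery disease as defined by CT coronary angiography", set against the standard 12-lead ECG. Section 7c plans on AUCs of 0.60 for ECG and 0.70 for cardiogoniometry, with 356 patients, a significance level of 0.05 and 80% power.

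On how cardiogoniometry is read, the Abstract says in general terms that "computer assisted analysis has allowed automated interpretation of vectorcardiography". The study procedures do not say that this study's result is the unedited software output, and they do not say who reads the ECG.

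**The concern.** When two tests are compared in the same patients, each result has to stand alone. Section 4c hides patient and imaging details, then closes the list. That leaves each test's result open to whoever reads the other. With both signals taken on one device in one session, an ECG reader could plausibly meet the cardiogoniometry result before deciding on a doubtful tracing.

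A reader who has seen a normal or abnormal classification may move a borderline ECG towards it. The comparator would then be ECG informed by cardiogoniometry, not the ECG that Objective 1 names. The two tests would agree more often than they should, the estimated difference would shrink, and power would fall. The secondary comparison of event hazards in Section 7b would use the same reads.

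**Working it through.** **Step 1: is cross-reading excluded anywhere?** Section 4c masks two kinds of information and then rules out further masking. An ECG or cardiogoniometry result is not imaging. It could be called a patient detail only by stretching the phrase, and the sentence that follows makes that reading weak. Sections 4a, 6c, 7a, 8d and 11a do not separate the two reads. Cross-reading is therefore permitted by the rule. Nothing shows that it is intended or certain.

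**Step 2: reproduce the plan's own figure.** The blinding rule rests on no number, and masking the reads would not change the sample size. The stated 356 serves only as a reference. The two-sided formula for two independent proportions, without continuity correction, gives

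n = [1.96 × √(2 × 0.65 × 0.35) + 0.84 × √(0.60 × 0.40 + 0.70 × 0.30)]² / 0.10² ≈ 356 per group.

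This matches the plan's figure exactly, but as a per-group number for independent groups, not as a paired AUC calculation. The 80% power is therefore taken as nominal below.

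**Step 3: illustrate an ECG read pulled towards cardiogoniometry.** Suppose a binary ECG read adopts the cardiogoniometry result in a random share q of patients. The documents do not give q, so it is an assumption. The gap becomes 0.10 × (1 − q). Discordance between the tests also falls by about (1 − q), so the test statistic falls by √(1 − q):

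Z = (1.96 + 0.84) × √(1 − q), power = Φ(Z − 1.96).

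| q | AUC gap | Power |
|---|---|---|
| 0% | 0.10 | 80% |
| 20% | 0.08 | 71% |
| 30% | 0.07 | 65% |
| 50% | 0.05 | 51% |

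**Step 4: cross-check with a paired AUC variance.** This uses the Hanley-McNeil variance with N = 356, prevalence 0.3 or 0.5, and AUC correlation 0 to 0.5. None of these prevalences or correlations is in the documents.

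- At the planned gap of 0.10, power is 0.58 to 0.87 (prevalence 0.3) or 0.69 to 0.94 (prevalence 0.5).
- At a gap of 0.05, power is 0.19 to 0.34 or 0.24 to 0.42.

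These are lower than the 51% in Step 3 partly because the correlation is held fixed as the gap narrows, whereas copying would also raise agreement. The two models agree on direction but not on size.

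**Step 5: the other direction, a cardiogoniometry read helped by the ECG.** Assume binormal tests with d = √2 × Φ⁻¹(AUC), which gives d₁ = 0.358 for ECG and d₂ = 0.742 for cardiogoniometry. The best combination has d′² = (d₁² + d₂² − 2r·d₁·d₂)/(1 − r²), and its AUC is Φ(d′/√2).

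| Correlation r (assumed) | Combined AUC |
|---|---|
| 0 | 0.720 |
| 0.3 | 0.703 |
| 0.5 | 0.700 |

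Against the planned 0.70, the gain is at most 0.02, and close to nothing once the two signals are moderately correlated.

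**The case against.** The strongest reply is that the text shows a possibility and not a bias. The documents do not say who reads the ECG, in what order, or whether the software shows both outputs together. That is correct. A reader might infer from Section 4c that the primary comparison is contaminated; the documents support only that contamination is not prevented.

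A reader might also infer that both tests are equally exposed. The Abstract describes cardiogoniometry as computer assisted and automated, and an algorithm cannot be swayed by an ECG read. The protocol does not settle whether the study uses unedited output, and Section 4c speaks of interpreting both findings. Even so, the realistic exposure is the human ECG read, and Step 5 shows little to gain on the other side.

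The expected bias narrows the difference, so it works against the study's hypothesis and would not manufacture a claim of superiority. This limits the harm, but a biased estimate of the primary comparison is still a defect.

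The damage need not be permanent. If the recordings are among the data stored and backed up under Section 8d, the tracings could be re-read masked. That would cost more than masking now.

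Finally, Section 11 says "ECG acquisition will be performed by the principal investigator or volunteer research staff", and nothing states that the recorder may not also be the reader. A reader might take this as part of the same fault. It is a separate question of how the masking to patient details already promised in Section 4c is carried out, and it does not bear on one test's result being visible to the reader of the other.

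**Conclusion.** The concern holds as a permitted risk. Section 4c does not require independent reads of the two tests whose accuracy is the primary comparison, and it rules out blinding beyond patient and imaging details. The main exposure is an ECG read pulled towards the cardiogoniometry result, with a smaller observed difference.

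The size is unknown. The range of 71% down to 51% power is an illustration. It rests on an assumed share of 20% to 50% of ECG reads following cardiogoniometry at random, and on the plan's 80% taken at face value. Neither the share nor the accuracy of that 80% is established by the documents. They do not support the stronger conclusions that the primary result is already invalid, that cardiogoniometry's accuracy would be materially inflated, or that the bias could never be repaired.

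Confidence is high that the rule permits cross-reading and low on how much it would matter. Severity: should-fix. How the CT is read is outside this point.

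**What to change.** In Section 4c, replace "No other blinding will be performed", as it applies to the two index tests, with wording such as:

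> The 12-lead ECG is read from coded tracings and its result locked before the cardiogoniometry output is opened. The cardiogoniometry result is the software's unedited automated output or, if read by a person, is read without the ECG result.

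This closes the main exposure and settles how the cardiogoniometry result is defined. It needs no extra patients or procedures and leaves the sample size unchanged. The existing team should be able to do it with coded batch reading. The documents do not say how many readers there are or whether the software can export a tracing without its own output, so both should be checked first. The cost is file handling and a delay before reads are available.

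### Follow-up events may be elicited and classified by someone who knows the baseline test results, which could bias the secondary hazard outcome

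*Combined protocol and SAP*

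**What the plan says.** Section 4, item c sets the whole blinding rule in two sentences. The first covers the tracings: "Interpretation of the ECG and cardiogoniometry findings will be performed without knowledge of any patient or imaging details". The second closes the subject: "No other blinding will be performed".

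Section 4, item b gives the only source of follow-up events: "The patients will be contacted by phone or email every 12 months to inquire about adverse cardiovascular events for the duration of the study". The same item sets the horizon: "The study duration will be 5 years".

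Those events feed a secondary outcome in Section 7, item b, namely "the hazard of adverse cardiovascular events determined by cardiogoniometry in comparison to standard 12-lead ECG and CT coronary angiography", which serves Objective 3. The primary outcome in Section 7, item a is separate: "Primary outcome variable is the diagnostic accuracy of cardiogoniometry to identify patients with coronary artery disease as defined by CT coronary angiography".

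Two other passages bear on who might see what. Section 8, item d keeps all patient data on one laptop "under personal supervision of the principal investigator", and Section 11 says "ECG acquisition will be performed by the principal investigator or volunteer research staff".

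The document does not say who makes the yearly contact or what that person has in front of them. It does not define an adverse cardiovascular event, and it describes no question script, record verification or adjudication.

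**The concern.** When an outcome comes from a conversation or an email exchange, two steps need judgement: how far to probe, and whether what the patient reports counts as an event. If either step goes differently for patients with an abnormal baseline test, an association between test and events appears even where none exists. No later analysis can separate it from a real one.

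The blinding that the plan does provide stops imaging and patient details from influencing the tracing reads. It does nothing in the other direction, where test results may influence the recording of events. Because item 4c rules out further blinding in so many words, protection at follow-up cannot be read in as implied.

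At stake is Objective 3, the comparison of prognosis by cardiogoniometry, ECG and CT. Section 3 states a favourable prior belief in cardiogoniometry. That is ordinary in a protocol, but it is a reason to keep its result away from event ascertainment.

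**Working it through.** **Step 1: passages side by side.**

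| Question | Where | Answer in the plan |
|---|---|---|
| Which readings are blinded? | 4c | ECG and cardiogoniometry only |
| Is anything else blinded? | 4c | No, stated expressly |
| How are events found? | 4b | Yearly phone or email inquiry |
| Which outcome uses them? | 7b, Objective 3 | Secondary hazard outcome |
| Does the primary outcome use them? | 7a | No; it is accuracy against CT |
| Who makes the contact, and what do they see? | nowhere | Not stated |
| What counts as an event, and who decides? | nowhere | Not stated |

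The passages show that knowledge of baseline results at follow-up is permitted. They do not show that it occurs.

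**Step 2: is there a figure in the plan to reproduce?** None for this outcome. The only calculated figure is the sample size of 356 in 7c, which belongs to the AUC comparison. It is used below only as a number of patients. The plan gives no event rate, no share of patients with an abnormal test and no ascertainment rate, so every size below rests on assumptions.

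**Step 3: illustration by acceptance of reports.** Assume a true ratio of 1.0. Let h be the share of reports needing judgement, equal in both groups, with the remainder always accepted. Let a and b be the acceptance rates of judgement-dependent reports in test-abnormal and test-normal patients.

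Apparent event ratio = (1 − h + h·a) / (1 − h + h·b)

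- h = 0.5, a = 0.8, b = 0.6: (0.5 + 0.40)/(0.5 + 0.30) = 0.90/0.80 = 1.125
- h = 0.5, a = 0.9, b = 0.5: (0.5 + 0.45)/(0.5 + 0.25) = 0.95/0.75 = 1.27
- h = 0.25, same two pairs: 0.95/0.90 = 1.06 and 0.975/0.875 = 1.11
- h = 0 (hard events only): 1.00

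These are ratios of event counts, close to hazard ratios when events are uncommon.

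**Step 4: check on the hazard scale.** Let p be the true event risk, and s1 and s0 the shares of events captured in test-abnormal and test-normal patients. With a true hazard ratio of 1:

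Apparent HR = ln(1 − p·s1) / ln(1 − p·s0)

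For example, p = 0.20, s1 = 0.95, s0 = 0.85: ln(0.81)/ln(0.83) = 0.2107/0.1863 = 1.13.

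The chance of a false two-sided significant result at the 5% level uses the Schoenfeld approximation, with mean shift √(D·f·(1 − f)) × |ln HR|. Here f is the share of patients with an abnormal test and D = 356 × [f·p·s1 + (1 − f)·p·s0] is the expected number of recorded events. For the example with f = 0.5, D = 356 × 0.18 = 64, the shift is √(64 × 0.25) × 0.123 = 0.49, and the false-positive chance is 7.8%.

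| Capture, abnormal vs normal | Apparent HR (p from 5% to 20%) | False-positive chance (f from 30% to 50%) |
|---|---|---|
| 95% vs 95% | 1.00 | 5% |
| 95% vs 85% | 1.12 to 1.13 | 5.5% to 8% |
| 95% vs 75% | 1.27 to 1.30 | 7% to 17% |

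The two approaches give similar distortions when the differences in ascertainment are similar.

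**The case against.** The strongest reply is that the plan never says the person making contact knows the results. A reader might infer from 4c that events will in fact be collected with results in hand; the text does not go that far. The passage in Section 11 concerns recording the tracings, not interpreting them or phoning patients. The laptop passage is a confidentiality measure, and one laptop does not preclude a separate contact list. This stands: knowledge of results is an inference, and the case rests on 4b and 4c together with the absence of any safeguard elsewhere.

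Next, bias in judging soft events presupposes that soft events count. If the outcome were confined to events such as death, there would be little room for it. This also stands, but it does not clear the plan. With no event definition, nothing confines the outcome in that way, and the gap adds to the problem.

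Third, the sizes have no anchor in the document, and the milder case moves the false-positive chance only from 5% to between 5.5% and 8%. They also concern one test at a time, whereas 7b compares three. If abnormal results overlap, or the caller reacts to any abnormal test, part of the distortion is shared. The effect on the comparison between tests has not been calculated. Stands in full.

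Finally, blinding the caller cannot reach the patient. The CT is done for clinical reasons, so patients and their physicians may know its result and report differently because of it. That limits what the remedy can achieve for CT. It has less force for cardiogoniometry, since Section 4, items d and e say care is otherwise unaffected and no management actions are involved.

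**Conclusion.** The point holds as a possible bias in a secondary outcome that is cheap to prevent. Item 4c expressly leaves follow-up unblinded, item 4b relies on unstructured inquiry, and nothing elsewhere makes up for it.

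Three stronger readings are not supported. The document does not show that results are known at follow-up, only that nothing prevents it. It does not show that the hazard outcome is biased, or in which direction; the apparent ratios of 1.13 and 1.27 depend wholly on the assumed true ratio of 1.0, the assumed half of reports needing judgement, and the assumed acceptance rates. And the primary outcome is not touched, because accuracy against CT uses no follow-up events.

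**What to change.** In Section 4, items b and c, replace the blanket exclusion of further blinding with text to this effect:

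- The yearly contact uses one fixed question list for all patients and a contact sheet that shows no cardiogoniometry, ECG or CT result.
- Each reported event is classified against a list of qualifying events fixed in advance, and the classification is locked before it is linked to the baseline results.

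The investigators should write the list of qualifying events. The report of the hazard outcome should also state the remaining limit, that reporting by patients may differ according to a CT result they already know.

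Existing staff can do this without extra visits or procedures. The cost is a scripted form, a contact list kept apart from the test results, and minor data-handling effort.
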